The Problem: While it is important to deliver texts at the right time and location, it is also necessary to deliver content that is individually and culturally relevant to optimize the impact on behavior. This has yet to be achieved in a weight-related mobile intervention for adolescents. Further, prior studies suggest efforts are needed to aid engagement as teens may ignore the texts over time if they are not viewed as varied or relevant.³¹

The Innovation: Our messages will be innovative in 3 ways: 1) they will be tailored to students’ individual characteristics and food preferences, 2) they will reflect the style, tone, vernacular, graphics and content preferred by the target population of AA students (determined by prior work in cultural tailoring and by focus group findings) and 3) recommended choices will be linked to menu options for their location (the healthiest options on the eating venues’ online menus will be identified in advance for use in the study).

or
occur
in
PiLR
the

C. APPROACH

This project will test an infrastructure to deliver culturally and individually tailored, evidence-based texts to adolescents at the time and location when they make food choices. During Phase 1 we will determine separately how well each of the functions can be achieved. A Phase 2 proposal will test effects on behavior, ensure long-term engagement, and determine how to achieve ‘scale-up’ that reaches any participant and accommodates an extended geography. As required in an STTR, “commercial development” will occur in Phase 3.

C.1. Integrated Mobile Phone Application (Aim 1)

To a) accurately identify when students are in their an eating venue, b) automatically deliver a tailored text message that prompts healthy choices, and c) receive annotated photos of students’ food choices.

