Message Testing Groups. A sample of the

adapted texts will be tested with the target population (2 groups with 6 to 8 students/group). Population, recruitment and consent/assent as above. Based on methods used successfully in our prior studies, students will use an OptionFinder audience response handset³⁴ to indicate for each text if they: (1) Really liked it = No Changes, (2) Thought it was O.K. = Improve, or (3) Did not like it = Reject. Messages with $\geq 60\%$ "really liked" and those with 60% "did not like" rating will be viewed as a consensus and not discussed further. All others will be discussed to elicit suggestions for improvements. The research team has extensive experience with testing and revising text messages for use in behavioral interventions. Students will receive a \$25 gift card for participating in this 2-hour group. [For this amendment, message testing groups will be replaced with a 5 – 10 member adolescent advisory board recruited. Key informants from the community (e.g., teachers our previous studies) will be asked to provide recommendations for possible members, and adolescents will also be selected from participants in the focus groups. The PM will contact the parents to describe the board. If they give verbal consent for their adolescent to participate, teens will be contacted to discuss the study and to assess their interest. Signed consent/assent will be obtained at the first meeting. Teens will receive a \$50 incentive per month of participation.

For convenience, these 90 minute meetings will be held in Detroit, Flint and Benton Harbor, and attendance via Skype or VSee teleconferencing will be offered. Meetings will be facilitated by the PI who works extensively with adolescents in clinical and research settings.

Tailored Menu Recommendations. Additional menus will be obtained from schools and popular fast food venues. The healthiest options will be identified from each venue for a variety of categories (e.g., salty foods, dairy

Table 1: MPOWERed Messages Library Message Types		
Message Type	Description	Example
Testimonials	Strategies others found helpful in weight loss	A teen says "TV was one of my favorite things, and I really didn't want to cut back. But, I dropped a few shows, and the truth is, I don't even miss them!"
Reflective Questions	Prompts to consider self-generated ideas	"What does being healthy mean for you? How does screen time fit with your goals?"

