Tailored Messages	Created to be tailored to participants' responses on baseline questionnaire.	Someone who eats breakfast daily might receive the message: "You eat breakfast every day. That's really smart. It means you're less likely to overeat later, especially at lunch. Keep up this great habit!"

foods, etc). The lists will be used to offer recommendations based on users' location and preferences (e.g., in McDonald's a student who said they like dairy foods on the baseline survey, might be asked to try a parfait). Following completion of Aims 1 and 2 the LIITA³H system (Figure 3) will be ready for pilot testing.

[figure not shown]
C.3. Pilot Trial (Aim 3)

We will study the feasibility, acceptability and use of the LIITA³H system via a pilot with four 1-week phases. [This amendment will test the app impact on frequency of visits to, and calories purchased from, FFR in a 6-month pilot].

We have shortened our study period time frame from 6 months to 1 month due to the COVID-19 pandemic.

C.3.a. Population and Recruitment. We will recruit 150 13-17 year olds, with a BMI>85th percentile who eat at FFR at least 3 times/week) from each of the 3 cities. Recruitment and consent/assent are as above. Students will receive two \$30 gift cards as an incentive for participation. A cell phone will be provided for those who do not own one. Payment will also be provided to cover the costs of internet access for those who need it.

Due to the COVID-19 situation that hampers physical contact, recruitment for the research study trial (to replace the in-person enrollment sessions due to the COVID situation) will be conducted virtually through UMHealthResearch.org and through a Facebook and Instagram advertising campaign managed by MICHRA and linked to our UMHealthResearch study page.

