Intervention Group 1 – Participants will be asked to keep the app running on their phone. They will receive a ping when the app identifies that they are in a fast food restaurant followed by a point of purchase prompt, tailored to their preferences and the options available at that location. If they are in a venue without a menu, general healthy suggestions will be provided (such as “consider choosing smaller portions” or “does this venue sell fruit?”). If the app does not ping when they enter a restaurant, they will be asked to register that location by tapping the ‘register location’ button on the app and entering the restaurant name. For detection errors, the appropriate stored venue criteria (location, geo-fence, time of day or dwell time) may be adjusted to improve detection. Users will also be asked to take a picture of any items they buy and to annotate it with information that would help to determine the nutrients in the food. Annotations may be audio, text, or made from a selection of descriptive buttons (e.g., to indicate small, medium or large sizes).

Control Group 2 – Participants in Control Group 2 will receive similar instructions to those given to group 1, but without receiving point of purchase prompts.

Control Group 3 – The Location Only Control Group 3 will only get information about location detection, and asked to register FFR if the app does not indicate with a ping that they have entered one. Their instructions will not discuss photo documentation of food or prompts as these features will not be active on their app.

During the study period, the participants will be contacted once per month by a research team member. Monthly calls will be added to help gather feedback from participants about the app. Study participants will be contacted by phone on three separate occasions, at times when the participants are not in school (e.g. after 4pm on weekdays or a weekend). If, for any reason, a research team member is unable to reach a study participant after three attempts, we will connect with the parent and/or research liaison (e.g. a staff member at the school or community organization we are working with) for assistance.

C.3.d Post Intervention Assessment

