As an exploratory analysis to assess for feasibility in preparation for a phase 2 trial, the U of M research team will apply MPOWER guidelines (regarding fat, fiber, sugar and calorie content) to assess whether students' food choices in week 4 were healthier than those in week 1 using the uploaded photos, accompanying student annotations, and nutrition information from venues' menus. We also will explore any associations between changes in food choice and student characteristics (i.e., sex, level of interest in making changes, BMI).

C.4. Project Timeline by Month

Project Activity	1	2	3	4	5	6	7	8	9	10	11	12
Aim 1												
Requirement planning and use case design	X	X		X								
Iterative Development (smartphone and server /web-service tools)		X	X	X	X	X						
Prototype mobile application and server						X	X					
Aim 2												
Collect menus and identify healthiest options	X	X	X	X								
Develop questionnaires, interview guides, and focus group prompts	X											
Recruit cultural tailoring focus groups		X	X									
Cultural tailoring focus groups			X	X								
Adapt and culturally tail messages				X	X							
Recruit message testing groups				X	X							
Message testing groups						X						
Revise messages						X	X					
Aim 3 - Pilot Testing and Reports												
Recruit for pilot							X	X	X			
Pilot study								X	X	X		
Data analysis and reporting									X	X		

the most robust services available, including augmented GPS, cellular triangulation and local RF (e.g., WiFi). An outcome of this Phase 1 will be to assess our ability to detect eating locations. However, for critical locations, such as a school cafeteria, we will be able to augment the current Google location database if failures are detected. The solution is simply to place a \$15 WiFi transmitter anywhere in the eating venue and register its unique “MAC” address with Google. The transmitter would be recovered at the end of the study. The transmitter will not be connected to the internet. More RF sources are being “discovered” and entered in the Google and similar databases constantly, so we expect that by the time Phase 2 work begins supplemental marking devices will not be needed. In any human research there is always the possibility of difficulty in recruiting. However, 3 schools have agreed to be trial schools. Further, in past studies, we have found adolescents are enthusiastic about participating.

C.6. Commercialization

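### Secondary Outcome 2 compares week 4 with week 1 and names no group; if applied to the amended randomised trial, it cannot show whether prompts improve food choices

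*Combined protocol and SAP*

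**What the plan says.** Section C.3.e, Secondary Outcome 2, applies the MPOWER guidelines on fat, fiber, sugar and calories to assess whether "food choices in week 4 were healthier than those in week 1 using the uploaded photos", together with annotations and menu data. It calls this exploratory and preparatory for a later trial, and names no group. Its second sentence relates changes in food choice to student characteristics.

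Section C.3 describes studying the system "via a pilot with four 1-week phases". In C.3.c, week 1 of that pilot was venue registration and location-linked messages started in week 3.

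The amendment text in C.3.c drops the first three weekly phases and places participants in one of three groups. A later note cuts the 6-month period to 1 month. C.3.b randomises participants on enrolment. The groups differ as follows:

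- Group 1: "They will receive a ping when the app identifies that they are in a fast food restaurant followed by a point of purchase prompt".
- Group 2: "similar instructions to those given to group 1, but without receiving point of purchase prompts".
- Group 3: "Their instructions will not discuss photo documentation of food or prompts as these features will not be active on their app".

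For the amendment, C.3.e plans a GEE for calories purchased (Group 1 versus Group 2) and one for visits (all three groups), each with a time-by-group interaction.

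**The concern.** In the original pilot, week 1 came before any location-linked message, so a week 4 versus week 1 contrast at least spanned the introduction of messages. In the amended trial that baseline is no longer described for Group 1. The cut to 1 month also makes weeks 1 and 4 the two ends of follow-up, so an analyst could apply the sentence as it stands.

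The result would be read as evidence on prompts, yet a trend common to prompted and unprompted students would look like improvement. A prompt effect already established in week 1 would not appear at all. The exploration of student characteristics uses the same change and inherits the problem. Fat, fiber and sugar are the most exposed, because this paragraph is the only planned analysis of them.

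**Working it through.** The plan gives no score, test, standard deviation, effect size or power for this outcome, so there is no stated figure to reproduce. The check is algebraic.

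**Inputs from the protocol.** Only Groups 1 and 2 submit photos, and only Group 1 receives prompts (C.3.c). The allocation ratio is not stated.

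**Assumptions.** Prompts can act in week 1. The time trend is the same in both groups. Higher scores mean healthier choices.

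**Model.** In week k, the Group 2 mean is m + T_k and the Group 1 mean is m + T_k + P·f_k. P is the full prompt effect and f_k is the share of it present in week k. Let T = T_4 − T_1, and let w be Group 1's share of the students pooled.

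- Group 2 change = T
- Group 1 change = T + P(f4 − f1)
- Pooled change = T + w·P(f4 − f1)
- Difference in changes between groups = P(f4 − f1)
- Group 1 minus Group 2 at week 4 = P·f4
- Group 1 minus Group 2 averaged over the month = P·mean(f)

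**Illustrative profiles** (assumed, linear over weeks 1 to 4, w = 0.5):

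| f1 to f4 | Group 1 change | Pooled change | Group difference, week 4 | Group difference, month |
|---|---|---|---|---|
| 1 to 1 | T | T | P | P |
| 0.5 to 1 | T + 0.5P | T + 0.25P | P | 0.75P |
| 0 to 1 | T + P | T + 0.5P | P | 0.5P |
| 1 to 0.5 | T − 0.5P | T − 0.25P | 0.5P | 0.75P |

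For w from 0.4 to 0.6, the pooled P terms are 0; 0.2 to 0.3; 0.4 to 0.6; and −0.2 to −0.3. T enters every before-after figure in full and no between-group figure.

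**With assumed values T = 0.2 and P = 0.4:**

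- No prompt effect at all (P = 0 instead): each group changes by 0.2, which is trend alone.
- Effect complete in week 1: Group 1 changes by 0.2 + 0.4 × (1 − 1) = 0.2, and so does Group 2. The week 4 group difference is 0.4.
- Effect fading to half: Group 1 changes by 0.2 + 0.4 × (0.5 − 1) = 0.0, Group 2 by 0.2, and the pool by 0.1. Yet Group 1 is still better by 0.4 × 0.5 = 0.2 in week 4.

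**Is adding group to the change enough?** No. The difference in changes is P(f4 − f1), which is 0 when the effect is complete in week 1. The level must be compared between groups.

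**Can the calorie GEE be reused unchanged?** Not safely, because it has one linear time term. Code time 0 to 3 with balanced weeks. For f = (0, 1, 1, 1) the mean is 0.75 and the slope is (−1.5 × 0 − 0.5 + 0.5 + 1.5)/5 = 0.3. The fitted week 4 difference is then (0.75 + 1.5 × 0.3)P = 1.2P, when the truth is P. For f = (1, 0.5, 0.5, 0.5) the mean is 0.625 and the slope is −0.15, giving (0.625 − 0.225)P = 0.4P when the truth is 0.5P. Week should therefore be categorical.

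**The case against.** The strongest reply is that this is legacy text. The document keeps old text and adds amendment text to it. The Primary Outcome and Secondary Outcome 1 have amendment paragraphs, while Secondary Outcome 2 has none. Dropping the first three weekly phases removes the very week 1 that the contrast needs. Stale text also survives close by: the C.4 timeline still lists message testing groups, although C.2.b says "message testing groups will be replaced with a" advisory board. This reading is plausible but not decisive. Some current text was changed in place with no amendment label, such as the three app versions in C.3.b and the advisory board input under Secondary Outcome 1. A missing label therefore does not show that a paragraph is retired.

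Second, the paragraph is exploratory and claims no causal effect, and the amended aim covers only calories and visits, which have group comparisons. This stands, and it limits the importance. A before-after change remains acceptable as description.

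Third, the premise that prompts act in week 1 is inferred. No start date is given, and early delivery may be incomplete: "For detection errors, the appropriate stored venue criteria (location, geo-fence, time of day or dwell time) may be adjusted to improve detection". This also stands. The closer f1 is to 0, the more of the prompt effect the change captures, but T remains in it.

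Fourth, fading is only a possibility. Section B.2 makes it conditional: "teens may ignore the texts over time if they are not viewed as varied or relevant". Tailoring is the protocol's answer to that risk.

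A reader might infer that the trial's main comparison is compromised, or that the sponsor has committed to a before-after analysis of the randomised trial. The documents support neither: the GEE models for calories and visits are separate, and the status of this paragraph is unresolved.

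**Conclusion.** The point holds conditionally. If Secondary Outcome 2 applies to the amended trial, its contrast mixes the full shared trend with P(f4 − f1) and cannot show whether prompts improve choices. If it belongs to the original pilot only, the fault is a missing label.

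The conclusion rests on prompts being able to act in week 1, which is inferred from silence, and on a trend shared between groups. T and P are unknown, so the profiles and numerical examples illustrate an identity and do not estimate a bias. Severity is minor, because the inference on calories and visits is unaffected. This is a cheap improvement.

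**What to change.** If the outcome is not kept for the amended trial, add one line saying that it applies to the original pilot only.

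If it is kept, replace the before-after contrast with a randomised Group 1 versus Group 2 comparison of each guideline element (fat, fiber, sugar, calories) in photographed purchases:

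- Fit a GEE clustered by participant, with week as a categorical factor and group-by-week terms.
- Report the group difference at week 4 and averaged over the month. Neither is larger under every profile.
- Label the analysis exploratory, with no multiplicity claim.
- Keep within-group week 1 to week 4 change as description only.
- Report photos per app-recorded visit by group and week. Prompts may alter uploading, and randomisation does not remove that bias.
- Fix the unit of analysis and the scoring of each element in advance.

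The cost is one line or one paragraph. Photos, visit counts and the GEE approach are already planned. Fat, fiber and sugar coding is planned only in this paragraph, so keeping the outcome means committing to that work.
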